### **Clinical Laboratory Tests**

Samples will be obtained at a minimum for the clinical laboratory tests listed in [Table 2](#) at the visits indicated in [Appendix C](#).

The blood samples for serum chemistry tests should be collected following a minimum 8-hour fast prior to study drug intake (with the exception of the Screening Visit, which may be non-fasting). Subjects whose visits occur prior to the morning dose of study drug should be instructed to fast after midnight until the blood sample is collected in the morning and thereafter take their study medications with food. Subjects whose visits occur following the morning dose of study drug should be instructed to fast after breakfast until the study visit occurs. At the Double-Blind Study Day 1 visit, a fasting blood sample should be collected prior to the first dose of study drug. Blood samples should still be drawn if the subject did not fast for at least 8 hours. Fasting or non-fasting status will be recorded in the source documents and on the laboratory requisition. The baseline laboratory test results for clinical assessment for a particular test will be defined as the last measurement prior to the initial dose of study drug.

A central laboratory will be utilized to process and provide results for the clinical laboratory tests.

During the DB Treatment Period, measures to prevent implicit un-blinding by laboratory results will be used. Specifically, the results of HCV RNA, ALT, AST, and bilirubin (indirect and total), will be blinded to the investigator, subject and AbbVie until the final scheduled DB Period visit (Week 8 or Week 16) or Premature D/C Visit, unless criteria for virologic failure or relevant predefined toxicity are met, in which case the relevant laboratory data will be un-blinded to the investigator, subject and AbbVie, see [Section 5.4.1.1](#), [Section 5.5.5](#) and [Section 6.1.7](#).

Instructions regarding the collection, processing, and shipping of these samples can be found in the laboratory manual provided by the central laboratory chosen for this study. The certified laboratory chosen for this study is Covance.

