- Baseline HCV RNA level ($< 1,000,000$ or $\geq 1,000,000$ IU/mL; $< 6,000,000$ or $\geq 6,000,000$ IU/mL; $< 10,000,000$ or $\geq 10,000,000$ IU/mL);
- Baseline HOMA-IR (< 2 or ≥ 2 mU \times mmol/L²);
- Baseline fibrosis stage (equivalent to Metavir F0 – F1, F2, F3, F4 [if applicable]);
- Baseline platelet count (< 100 or $\geq 100 \times 10^9$ /L);
- Baseline albumin (< 35 or ≥ 35 g/L);

- Baseline creatinine clearance (Cockcroft-Gault) (< 60 , ≥ 60 to < 90 , or ≥ 90 mL/min);
- Baseline eGFR (C-MDRD) (< 60 , ≥ 60 to < 90 , or ≥ 90 mL/min/1.73 m²);
- Baseline total bilirubin (< 34.2 or ≥ 34.2 umol/L);
- Baseline total INR (continuous and < 1.7 or ≥ 1.7);
- History of diabetes (yes/no);
- History of bleeding disorders (yes/no);
- History of depression or bipolar disorder (yes/no);
- History of cardiovascular disease (yes/no);
- Baseline metabolic syndrome (yes/no);
- Injection drug use (yes, within last 12 months; yes, more than 12 months ago; or no);
- Baseline stable opiate substitution use (yes/no);
- Baseline hepato-protectant medication use (as determined by investigator on concomitant medication eCRF, yes/no);
- Tobacco use (user, ex-user, or non-user);
- Alcohol use (drinker, ex-drinker, or non-drinker);
- Concomitant use of Proton Pump Inhibitors (PPIs) (yes/no).

The demographic and baseline characteristics specified above, along with the following, will be summarized for subjects with HCV/HIV co-infection at Screening for the overall safety population and for the geographic region of China:

- HIV-1 treatment status (antiretroviral therapy [ART]-Naïve, ART-Treated),
- HIV-1 ART regimen (e.g., raltegravir [RAL], dolutegravir [DTG], rilpivirine [RPV]) for those receiving ART (as determined by investigator on concomitant medication eCRF) at baseline,
- Baseline CD4+ T-cell count (continuous; and < 200 , 200 to < 350 , 350 to < 500 , or ≥ 500 cells/mm³).

Any concomitant medication coded to the WHO Drug Dictionary ATC code of A02BC will be counted as a PPI.

If the IL28B genotype result is not available from a sample collected during the Screening period, then a result available from a sample collected at any time during the study will be used to summarize IL28B genotype.

HOMA-IR is defined as fasting glucose (mmol/L) \times fasting insulin (μ IU/mL) \div 22.5. Subjects who do not have concurrent fasting glucose and fasting insulin values at baseline will be excluded from the summary of baseline HOMA-IR.

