Hematology and chemistry data values will be categorized as low, normal, or high based on the normal ranges of the laboratory used for each sample. Shift tables from baseline to minimum value and from baseline to maximum value during the DB and OL Treatment Periods will be created for each treatment arm. The shift tables will cross-tabulate the frequency of subjects with baseline values below/within/above the normal range versus minimum/maximum post-baseline values below/within/above the normal range.

The laboratory parameters listed in [Table 15](#) will be categorized according to the toxicity grades defined in the table. The number and percentage of subjects with a maximum toxicity grade of 1, 2, 3 or 4 during treatment (DB treatment and OL treatment summarized separately) will be calculated for each treatment arm. To be counted, the post-baseline value must have a toxicity grade that is more extreme than the toxicity grade corresponding to the baseline value. For each laboratory parameter in [Table 15](#), the summary will also include the number and percentage of subjects with a maximum of at least Grade 3 for each treatment arm. For summaries of data collected during the DB Treatment Period, the difference in rates between the 2 arms (Arm A minus Arm B), and

the 2-sided 95% CI for the rate difference using the Wilson score method for a difference in proportions will be presented.¹² These summaries will also be presented for the set of HCV/HIV co-infected subjects (determined at Screening) within the populations/groups specified in Section 11.1.

A listing of all relevant laboratory parameters will be provided for each subject who had an increase to Grade 2 or higher for any laboratory variable in Table 15.

For the assessments of hepatotoxicity based on single and multiple laboratory parameters, the number and percentage of subjects meeting the criterion during treatment will be calculated for each criterion. A listing of all ALT, AST, total, indirect and direct bilirubin, ratio of direct to total bilirubin, and alkaline phosphatase values will be provided for each subject who met any of the single or multiple criteria defined above. The listings will be reviewed to assess bilirubin (e.g., mixed or direct predominance) and temporal relationships for subjects with $ALT > 3 \times ULN$ (or ALT Grade 2+) and total bilirubin $\geq 2 \times ULN$.

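### Glucose and triglyceride toxicity is graded on all samples whatever their recorded fasting status, so meal effects can inflate the within-arm rates of worsening

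*SAP*

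**What the plan says.** Protocol 5.3.1.1 (Clinical Laboratory Tests) starts with a general rule: "The blood samples for serum chemistry tests should be collected following a minimum 8-hour fast prior to study drug intake". Screening is exempt. For Day 1 it says "a fasting blood sample should be collected prior to the first dose of study drug". It then treats two kinds of visit separately. Subjects seen before the morning dose "should be instructed to fast after midnight until the blood sample is collected in the morning". For the others: "Subjects whose visits occur following the morning dose of study drug should be instructed to fast after breakfast until the study visit occurs". Short fasts do not stop the draw: "Blood samples should still be drawn if the subject did not fast for at least 8 hours". The status is kept: "Fasting or non-fasting status will be recorded in the source documents and on the laboratory requisition". Protocol 5.3.1.2 has active drug and placebo both taken with food.

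The SAP grades glucose and triglycerides by the limits in Table 15 (11.3.1), which set no fasting condition. SAP 6.2 keeps every value for shifts and graded values. SAP 11.3.2 counts a subject by maximum grade on treatment, with one condition: "To be counted, the post-baseline value must have a toxicity grade that is more extreme than the toxicity grade corresponding to the baseline value". The laboratory baseline is the last non-missing pre-dose value, again with no fasting condition, and the same value serves the double-blind, open-label and post-treatment summaries.

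Fasting does matter elsewhere in the SAP. For HOMA-IR (7.1): "Subjects who do not have concurrent fasting glucose and fasting insulin values at baseline will be excluded from the summary of baseline HOMA-IR". Table 12 also names fasting glucose as a metabolic-syndrome criterion.

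**The concern.** Glucose and triglycerides are the graded chemistry values for which a recent meal matters most. If the baseline is fasting and a later sample is not, the rise after the meal is compared with a fasting grade and can be tabulated as worsening. The maximum-grade rule adds to this, since one sample after a meal is enough. Mean changes and shift tables for the same two parameters have the same gap.

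At stake are the reported rates of hyperglycaemia and hypertriglyceridaemia in each arm, the precision of the between-arm difference, and the open-label column for Arm B. A subject who reaches Grade 2 also enters the per-subject laboratory listing in SAP 11.3.2. No efficacy endpoint and no sample-size calculation is affected.

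**Working it through.** The plan states no figure on this point, so there is nothing to reproduce. The check has a textual part and two illustrations.

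**Text.** The after-breakfast instruction sets no minimum interval. A late visit can still meet 8 hours; an earlier one cannot. A sample taken after the morning dose also cannot satisfy the general rule that it precede study drug intake, so the two sentences need to be reconciled. Since the protocol both allows short-fast samples and records them, it expects some. Nothing in SAP 11.3 separates them out.

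**Illustration 1: within-arm triglyceride rates.** From the documents: the Table 15 limits of 1.71, 3.42, 5.7 and 11.4 mmol/L, and four on-treatment visits (Weeks 1, 2, 4 and 8). Assumed, not from the documents:

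- fasting median 1.2 mmol/L, lognormal, between-subject CV 45%, within-subject CV 20%, with log-scale variance ln(1 + CV²);
- a fasting baseline;
- a share of subjects sampled after a meal at all four visits, with values multiplied by 1.15 or 1.30.

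A subject counts if the maximum on-treatment grade exceeds the baseline grade. Each setting used 400,000 simulated subjects. Ranges run from a 15% to a 30% meal rise.

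| Share sampled after a meal | Any worse grade | Worsening to Grade 2 or higher |
|---|---|---|
| 0% | 18.6% | 2.2% |
| 10% | 19.9% to 21.2% | 2.5% to 2.9% |
| 30% | 22.6% to 26.6% | 3.1% to 4.3% |
| 60% | 26.5% to 34.6% | 3.9% to 6.3% |

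Worsening to Grade 3 or higher is 0.11% with no meals, 0.18% to 0.29% at 30% and 0.24% to 0.48% at 60%. In 336 Arm A subjects the largest excess is 336 × (0.0048 − 0.0011) ≈ 1.2 subjects. In the most extreme setting the any-grade excess is 34.6 − 18.6 = 16.0 points, of which 6.3 − 2.2 = 4.1 points reach Grade 2 or higher. About three quarters of the excess is therefore Grade 1.

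**Illustration 2: the double-blind difference.** Let s be the share of subjects in each arm with post-breakfast visits, q the per-visit chance that a meal alone lifts the grade, and r the true rate of worsening. Both s and q are assumed. Over four visits the meal-only probability is f = s × (1 − (1 − q)⁴), and the observed rate is r + (1 − r) × f. The expected difference between arms becomes (r_A − r_B) × (1 − f). With n = 336 and 168, and Wald half-widths:

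| s, q | f | Observed rate if true rate is 5% | True 5.0-point difference (10% v 5%) becomes | 95% CI half-width, points |
|---|---|---|---|---|
| no meals | 0 | 5.0% | 5.0 | 4.6 |
| 10%, 5% | 0.019 | 6.8% | 4.9 | 5.1 |
| 30%, 10% | 0.103 | 14.8% | 4.5 | 6.8 |
| 50%, 20% | 0.295 | 33.0% | 3.5 | 8.8 |

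If r_A = r_B, the expected difference is exactly 0 for any f.

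**The case against.** The strongest reply is that the design already protects the comparison that matters. Both arms follow the same food rule and the same sampling instructions, under randomisation and blinding, and SAP 11.3.2 reports the rate difference with a confidence interval. This stands. A reader might infer that meal effects would appear as a drug effect in the double-blind period; the documents do not support that, and Illustration 2 gives an expected difference of 0 when there is no true effect.

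A reader might also infer that many on-treatment samples are non-fasting by instruction. No section gives the share of visits held after the morning dose, and the general 8-hour rule covers all chemistry samples after Screening. Only some such samples can be said to be allowed.

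Nor is the baseline always fasting. A missing Day 1 value falls back to Screening, which may be non-fasting, and a non-fasting Day 1 sample is still used. That can offset the bias in some subjects, but it is also a reason to apply the flag at baseline.

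For the open-label period, it goes too far to say the inflation will read as a drug effect. These are the Arm B subjects, whose own placebo-period column carries the same baseline and grading rule, and Protocol 8.1.5 plans no open-label comparisons. There is still no concurrent control.

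Finally, keeping all values is a deliberate safety choice, fasting status is a post-randomisation variable, and HOMA-IR needs fasting values by definition, so it is a weak precedent. These are good arguments against replacing the all-sample rows. They do not tell against adding fasting-only rows.

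**Conclusion.** The point holds as a cheap improvement. SAP 11.3.2 and Table 15 ignore a recorded status that bears directly on two graded parameters, so meal-related rises can be counted as worsening from an intended fasting baseline. The expected consequences are higher within-arm rates, mainly Grade 1 and some Grade 2; a modest loss of contrast if a real difference exists (a true 5.0 points becoming 4.9 to 3.5, with a wider interval); and open-label rates with the same inflation and no concurrent control.

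The size is illustrative. It rests on an assumed triglyceride distribution, meal effect and share of non-fasting samples, none of which the documents give. No corresponding calculation was made from a glucose distribution. Under these assumptions Grade 3 or higher triglyceride rates barely move, and no primary or secondary endpoint is involved.

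**What to change.** In SAP 11.3.2, for glucose and triglycerides only, present the toxicity-grade tables, shift tables and mean changes restricted to samples flagged fasting, at baseline and on treatment, beside the all-sample version. Keep the all-sample rows so that no severe value is lost. Mark non-fasting values in the listing of subjects with an increase to Grade 2 or higher. State how values with unknown fasting status are handled.

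In Protocol 5.3.1.1, reconcile the general 8-hour, pre-dose rule with the after-breakfast instruction.

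The cost is a filter on a status the protocol already records, plus a few extra table rows. The fasting rows will hold fewer samples. Fasting status may be missing for local-laboratory values, which SAP 11.3 includes, and its transfer from the requisition to the analysis database should be confirmed.

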11.4 Analysis of Vital Signs and Weight

11.4.1 Variables and Criteria Defining Abnormality

Vital sign variables are body temperature, sitting systolic blood pressure, sitting diastolic blood pressure, sitting pulse rate, and body weight.

The criteria for potentially clinically significant (PCS) vital sign findings are presented in Table 16.

Table 16. Criteria for Potentially Clinically Significant Vital Sign Values

Test/Measurement	Very Low (VL)	Very High (VH)
Systolic Blood Pressure	≤ 90 mmHg AND A decrease of ≥ 20 mmHg from baseline	≥ 180 mmHg AND An increase of ≥ 20 mmHg from baseline
Diastolic Blood Pressure	≤ 50 mmHg AND A decrease of ≥ 15 mmHg from baseline	≥ 105 mmHg AND An increase of ≥ 15 mmHg from baseline
Pulse Rate	≤ 50 bpm AND A decrease of ≥ 15 bpm from baseline	≥ 120 bpm AND An increase of ≥ 15 bpm from baseline
Weight	A decrease of $\geq 15\%$ from baseline	An increase of $\geq 15\%$ from baseline
Body Temperature		$> 38.3^{\circ}\text{C}$ AND An increase of $\geq 1.1^{\circ}\text{C}$ from baseline

11.4.2 Statistical Methods

Vital signs will be summarized by treatment arm at each visit during the DB Treatment Period and separately for Arm B subjects in the OL Treatment Period. Also, vital signs collected during the Post-Treatment Period will be presented for Arm A of the safety population and separately for the OL population.

The baseline value for vital signs will be the last measurement on or before the day of the first dose of DB study drug. The same baseline value will be used for all summaries of the data from the DB, OL, and Post-Treatment Period visits.

Changes from baseline to each post-baseline visit, including applicable post-treatment visits, will be summarized. For DB Treatment Period visits and for Post-Treatment visits for Arm A, each vital sign parameter will be summarized with the sample size; baseline mean; visit mean; and change from baseline mean, standard deviation, and median. The differences between the active and placebo arms in the DB Treatment Period will be analyzed using an ANOVA model with treatment arm as the factor. The difference between the treatment arms (Arm A minus Arm B) in mean change from baseline along with the corresponding 95% CI, standard error, and *P* value will be presented. For OL Treatment Period visits and Post-Treatment visits for Arm B, each vital sign parameter

will be summarized with the sample size; baseline mean; visit mean; and change from baseline mean, standard deviation, minimum, median, and maximum.

The number and percentage of subjects with on-treatment values (DB treatment and OL treatment summarized separately) meeting the specified criteria for PCS vital sign values (Table 16) will be calculated for each treatment arm. A post-baseline value must be more extreme than the baseline value to be considered a PCS finding. A separate listing will be provided that presents all vital sign values for the subjects meeting PCS criteria during treatment.

11.5 Analysis of HIV-1 RNA and Flow Cytometry Data

Plasma HIV-1 RNA will be measured by the central laboratory using the Roche COBAS AmpliPrep/COBAS TaqMan HIV-1 Test, version 2.0. For specimens with HIV-1 RNA results that are detectable but not quantifiable, the results are reported as "< 20 CP/ML HIV-1 RNA DETECTED;" for specimens with no HIV RNA detected, the results are reported as "NO HIV-1 RNA DETECTED." Subjects will also have blood samples drawn and archived. These samples may be used for other analyses including drug resistance testing. These samples may be tested at the discretion of AbbVie.

For the HCV/HIV co-infected subjects (determined at Screening) who are on HIV-1 ART at initiation of DB study drug, the numbers and percentages of subjects with 2 consecutive HIV-1 RNA values ≥ 200 copies/mL during the DB and OL Treatment Periods will be calculated for each treatment arm; only data from the central laboratory will be included in these analyses. A listing of subjects with a plasma HIV-1 RNA value ≥ 200 copies/mL at any baseline or post-baseline visit during the study will be provided. Data from the central and local laboratory will be included in the listing.

For the HCV/HIV co-infected subjects (determined at Screening), changes from baseline to each post-baseline visit, including applicable post treatment visits, in CD4+ T-cell count (absolute and percentage), CD8+ T-cell count (absolute and percentage), and lymphocytes (count) will be summarized for each treatment arm. For DB Treatment

Period visits, for Post-Treatment visits for Arm A, and for OL Treatment Period visits and Post-Treatment visits for Arm B, each protocol-specified laboratory parameter will be summarized with the sample size; baseline mean; visit mean; and change from baseline mean, standard deviation, minimum, median, and maximum.

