##### **For HCV/HIV-1 Co-Infected Subjects on Stable ART**

The criteria for failure to maintain HIV virologic suppression is as follows:

- HIV-1 RNA  $\geq$  200 copies/mL confirmed on 2 consecutive tests at least 2 weeks apart, in a subject compliant with their HIV ART therapy.

At the time a confirmatory HIV-1 RNA is drawn, a sample for HIV-1 genotypic resistance testing may also be obtained; this sample may be analyzed if the subject's repeat plasma HIV-1 RNA is  $\geq$  500 copies/mL. A subject should remain on HCV study drug treatment and his/her current ART regimen while the failure to maintain HIV virologic suppression is being confirmed. A confirmatory HIV-1 RNA and HIV-1 genotypic resistance blood draw can be done as an unscheduled visit. However, if this blood draw falls on the date of a scheduled study visit ([Appendix C](#)), only a single HIV-1 RNA and HIV-1 genotypic resistance blood draw needs to be performed at this visit.

Clinical management of failure to maintain HIV-1 virologic suppression during the study (DB and OL Treatment Periods and Post-Treatment Period) will be handled by the site investigator according to current HIV treatment guidelines and local standard of care.

If the investigator wishes to change the HIV-1 ART regimen for a subject, it must be discussed with the AbbVie TA MD prior to the change being made, unless the change is being made to address an immediate safety concern.

During the DB or OL Treatment Periods, subjects with confirmed failure to maintain HIV-1 RNA suppression should continue study drug (active or matching placebo) treatment unless there is a requirement for prohibited concomitant medications (see Section 5.2.3.2 and Section 5.2.3.4) to construct a new HIV ART regimen.

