### **8.1.5.3 HIV-1 RNA Data**

For the HCV/HIV co-infected subjects who were on stable HIV-1 ART at initiation of double-blind study drug, the numbers and percentages of subjects with 2 consecutive HIV-1 RNA values  $\geq 200$  copies/mL during the DB and OL Treatment Periods will be calculated for each treatment arm.

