c. The last value within the window will be used to define the Final DB Treatment Visit value. For Arm A subjects, the upper bound of this Final window is DB Study Drug End Day 2. For Arm B subjects, it is the earlier of DB Study Drug End Day 2 and the day of first dose of OL active study drug. DB Study Drug End Day 0 is defined as the day of the last dose of DB study drug.

Note: Time windows specified in this table are for HCV/HIV co-infected subjects only. For all windows, data must be on or before DB Study Drug End Day 2, and for Arm B subjects, data must also be on or before the day of first dose of OL active study drug. The result closest to the scheduled time point will be used. Flow cytometry samples are collected at DB Day 1, DB Week 4, DB Week 12 (if 16-week treatment), and DB End of Treatment Visit.

Table 9. Analysis Time Windows for HIV-1 RNA and Flow Cytometry Measurements (OL Treatment Period)

Scheduled Visit ^a	Nominal Day (Active Study Day)	Time Window (Active Study Day Range)
OL Week 1	7	2 to 10
OL Week 2	14	11 to 21
OL Week 4	28	22 to 42
OL Week 8	56	43 to 70
OL Week 12 ^b	84	71 to 98
OL Week 16 ^b	112	99 to 126
Final OL Treatment Visit ^c	2 to ≤ 2 days after last dose of OL study drug	

- a. OL visits are applicable for subjects randomized to Arm B (placebo) who received at least one dose of OL active study drug.
b. For 16-week treatment only.

Table 9. Analysis Time Windows for HIV-1 RNA and Flow Cytometry Measurements (OL Treatment Period) (Continued)

c. The last value within the window will be used to define the Final OL Treatment Visit value. The upper bound of this Final window is Active Study Drug End Day 2. Active Study Drug End Day 0 is defined as the day of the last dose of active study drug.

Note: Time windows specified in this table are for HCV/HIV co-infected subjects only. For all windows, data must be on or before Active Study Drug End Day 2. The result closest to the scheduled time point will be used. Flow cytometry samples are collected at OL Week 4, OL Week 12 (if 16-week treatment), and OL End of Treatment Visit.

Analyses of these data will not be included in the primary CSR.

Table 10. Analysis Time Windows for HIV-1 RNA and Flow Cytometry Measurements (Post-Treatment Period)

Scheduled Visit ^a	Nominal Day (Active Study Drug End Day)	Time Window (Active Study Drug End Days Range)
Post-Treatment Week 4	28	3 to 56
Post-Treatment Week 12	84	57 to 126
Post-Treatment Week 24 ^b	168	127 to 999

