10.0 Efficacy Analysis

10.1 General Considerations

General Considerations

Treatment effects will be evaluated based on a 2-sided significance level of 0.050 (when rounded to three decimal places), and all efficacy analyses will be performed on the ITT population randomized to Arm A, unless otherwise specified.

Missing data will be imputed as described in Section 6.3 for analyses of the HCV RNA endpoints of SVR.

Plasma HCV RNA levels will be determined for each sample collected by the central laboratory using the Roche COBAS[®] AmpliPrep/COBAS[®] TaqMan[®] HCV Quantitative Test, v2.0. The lower limit of detection (LLOD) and lower limit of quantification (LLOQ) for this assay (regardless of genotype) are both 15 IU/mL.

HCV RNA results that are detectable but not quantifiable are reported as "< 15 IU/ML HCV RNA DETECTED" and those that are undetectable are reported as "HCV RNA NOT DETECTED" in the database.

The notation "HCV RNA < LLOQ" is used to represent all HCV RNA values < 15 IU/mL, including values reported as "HCV RNA NOT DETECTED" or "< 15 IU/ML HCV RNA DETECTED." HCV RNA \geq LLOQ are all quantifiable values of 15 IU/mL or greater.

IL28B rs12979860 will be resulted as C/C, C/T, or T/T by the central laboratory.

Definitions for Efficacy Endpoints

A confirmed quantifiable value during treatment is defined as any two consecutive HCV RNA measurements \geq LLOQ (or 100 IU/mL for **Breakthrough**), either both during treatment or at the final treatment measurement and the next consecutive post-treatment measurement. A confirmed quantifiable post-treatment value is defined as any two consecutive post-treatment HCV RNA measurements \geq LLOQ.

Breakthrough = confirmed HCV RNA \geq 100 IU/mL after HCV RNA < LLOQ during the Treatment Period; or confirmed increase from nadir in HCV RNA (two consecutive HCV RNA measurements > 1 log₁₀ IU/mL above nadir) at any time point during the Treatment Period. A single breakthrough value (\geq 100 IU/mL or > 1 log₁₀ above nadir) followed by lost to follow-up also will be considered a breakthrough (i.e., will not require confirmation).

EOT failure = HCV RNA \geq LLOQ at end of treatment with at least 6 weeks of treatment, where the HCV RNA value must be collected on or after Study Drug Day 36 and study drug duration \geq 36 days.

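### The HIV-rebound percentage normally omits a rebound first seen at the last on-treatment visit and confirmed after treatment, because both values must fall within the treatment periods

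*SAP*

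**What the plan says.** SAP 11.5 takes the co-infected subjects who were on ART when double-blind (DB) drug began, and reports the numbers and percentages with "2 consecutive HIV-1 RNA values ≥ 200 copies/mL during the DB and OL Treatment Periods will be calculated for each treatment arm". It adds that "only data from the central laboratory will be included in these analyses". Protocol 8.1.5.3 plans the same summary with the same period limit ("copies/mL during the DB and OL Treatment Periods will be calculated for each treatment arm") but does not restrict the laboratory. The SAP's list of changes from the protocol (12.1) does not record that restriction; its item 13 only names the assay.

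The note to SAP Table 8 states: "For all windows, data must be on or before DB Study Drug End Day 2". Table 9 sets the matching bound for the open-label (OL) period. Table 10 defines post-treatment HIV-1 RNA windows, but 11.5 plans no post-treatment count.

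Protocol 5.4.1.2 describes failure to maintain suppression as HIV-1 RNA of at least 200 copies/mL "confirmed on 2 consecutive tests at least 2 weeks apart, in a subject compliant with their HIV ART therapy". Appendix C allows the repeat at an unscheduled visit, but not sooner than 2 weeks after the first result.

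For HCV RNA, SAP 10.1 accepts a confirming pair "either both during treatment or at the final treatment measurement and the next consecutive post-treatment measurement", and SAP 6.3 falls back on a local-laboratory value when the central one is missing.

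SAP 11.5 also plans a listing of subjects with a "plasma HIV-1 RNA value ≥ 200 copies/mL at any baseline or post-baseline visit during the study will be provided", and says: "Data from the central and local laboratory will be included in the listing".

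**The concern.** The count requires both values of the pair to lie inside the treatment periods. At the final on-treatment visit the first value can lie inside, but a repeat that respects the protocol's 2-week gap cannot. A rebound first seen at that visit and confirmed at Post-Treatment (PT) Week 4 meets the virologic part of the protocol's criterion, yet normally does not enter the percentage. A confirming result that exists only from a local laboratory is also left out.

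This is the only planned rate of HIV rebound in the trial. With so few subjects, one case is the difference between 0% and a non-zero rate, and a reader of the summary table could take 0% to mean that no confirmed rebound occurred. The SAP solves the same end-of-treatment problem for HCV RNA, and SAP 10.8 triggers HIV resistance analysis (South Korea and Singapore only) on a confirmed rise at any time after study start. That suggests a gap in the rule rather than a deliberate choice.

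**Working it through.** The plan states no figure to reproduce; the check is day arithmetic.

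**Inputs**
- DB HIV-1 RNA draws: Weeks 2, 4 and 8, plus 12 and 16 for 16-week courses (protocol Appendix C).
- Nominal days: 14, 28, 56, 84 and 112 (SAP Table 8).
- Last dose L: assumed to be Day 56 or Day 112.
- Cut-off: L + 2 (SAP Table 8 note).
- Minimum gap to the repeat: 14 days (protocol 5.4.1.2 and Appendix C).

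**Rule.** A first value on day v can be confirmed in time only if v + 14 ≤ L + 2.

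| Course | First value ≥ 200 | Earliest repeat | Cut-off | In time? |
|---|---|---|---|---|
| 8 weeks | Day 14 | Day 28 | Day 58 | Yes |
| 8 weeks | Day 28 | Day 42 | Day 58 | Yes |
| 8 weeks | Day 56 | Day 70 | Day 58 | No, 12 days late |
| 16 weeks | Day 84 | Day 98 | Day 114 | Yes |
| 16 weeks | Day 112 | Day 126 | Day 114 | No, 12 days late |

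The latest first detection that can be confirmed in time is 58 − 14 = Day 44 for 8 weeks and 114 − 14 = Day 100 for 16 weeks. The protocol's definition of terms ends the Treatment Period at the last dose, which would move each cut-off 2 days earlier. For a Day 56 value to be confirmable, the last dose would have to be on Day 68 or later (68 + 2 = 70).

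**A confirming sample is already drawn.** PT Week 4 is nominally 56 + 28 = Day 84, and its window (End Days 3 to 56, SAP Table 10) is Days 59 to 112. Day 84 is 28 days after Day 56, so it satisfies the gap.

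**Arm B.** OL dosing starts on about Day 57, so OL Weeks 1 and 2 fall on about Days 63 and 70, which are 7 and 14 days after DB Week 8. A DB Week 8 rise can therefore be confirmed on treatment if the DB and OL periods are read as continuous. The same gap returns at the end of OL treatment.

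**Size.** SAP Table 1 expects 10 + 6 + 10 + 2 + 4 = 32 co-infected subjects in Arm A. The number on ART is not given, so smaller denominators are assumptions. Wilson 95% limits are [p + z²/2n ± z√(p(1−p)/n + z²/4n²)] / (1 + z²/n), with z = 1.96.

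| n | No case counted | One case counted |
|---|---|---|
| 32 | 0% (0 to 10.7) | 1/32 = 3.1% (0.6 to 15.7) |
| 20 (assumed) | 0% (0 to 16.1) | 1/20 = 5.0% (0.9 to 23.6) |
| 10 (assumed) | 0% (0 to 27.8) | 1/10 = 10.0% (1.8 to 40.4) |

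**The case against.** The strongest reply is that the case is reported. The listing covers any single value of 200 copies/mL or more, at any visit and from either laboratory. With about 32 subjects or fewer, a reader can find every omitted case. That stands, and it limits the harm. The listing does not classify confirmed failures or correct the percentage, however.

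Second, the SAP follows protocol 8.1.5.3 on the period limit, so this is not a departure by the SAP. That also stands: the limit is common to both documents, and only the laboratory restriction is new. The criterion in 5.4.1.2 sits in the section on removing subjects from therapy and carries an ART-compliance condition that neither summary uses, so the count was never an exact copy of it.

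Several stronger readings are tempting, but the documents do not support them:
- *A Week 8 rebound can never be counted.* SAP 11.5 does not repeat the 2-week gap. On its wording alone, a central repeat on Day 57 or 58 would count, although Appendix C does not allow a repeat that early. Even with the gap, the Week 8 window opens on Day 43, and a draw on Day 43 or 44 can be confirmed by Day 58.
- *The second half of treatment contributes nothing.* A Week 4 value confirmed at Week 8 is counted.
- *Half of all rebounds are lost.* The share (56 − 28)/56 = 50% needs onset to be uniform over 56 days and detection only at nominal visits. Nothing in the documents supports uniform onset.
- *The rule favours Arm A over Arm B.* This depends on pairing values across the DB and OL periods, which 11.5 does not settle. If the periods are reported separately, as the SAP does for adverse events and laboratory grades, Arm B has the same gap at DB Week 8. No between-arm test is planned.

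**Conclusion.** The point holds in limited form. At the last on-treatment visit of any active course, in either arm, a first value of 200 copies/mL or more that is confirmed only post-treatment is normally left out of the stated percentage. It remains visible in the listing. The central-laboratory limit can remove further cases; how often is unknown, because the documents do not say that repeats will be run locally.

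One omitted case changes the Arm A rate by 3.1 percentage points at n = 32, and by more as the ART-treated number falls. SAP 12.1 already anticipates fewer co-infected subjects than planned. The result assumes a last dose on the nominal day, a draw on the nominal final visit day, and a repeat that respects the 2-week gap. The primary endpoints and the sample size are not affected.

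**What to change.** In SAP 11.5:

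1. Keep counting on-treatment consecutive pairs as now.
2. Also count a subject whose final on-treatment value (to End Day 2) is at least 200 copies/mL and whose next post-treatment or unscheduled value is also at least 200 copies/mL, matching the SAP 10.1 rule for HCV RNA.
3. Use a local-laboratory value when no central value exists, as SAP 6.3 does for HCV RNA. If the central-only limit is kept instead, record it in 12.1 with a reason.
4. Assign each Arm B event to the period, DB or OL, of its first value.
5. State whether the 2-week gap applies to the count. If it does, let the confirming value be the first one at least 2 weeks later with no intervening value below 200 copies/mL. Requiring the very next value to be 2 weeks later would disqualify the OL Week 1 and Week 2 pair, 7 days apart, which the SAP now counts, and could lower the count.

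The cost is a few sentences and minor programming. No new samples are needed, since HIV-1 RNA is already drawn at PT Weeks 4, 12 and 24. The reported rate may rise slightly.
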